4. LIST OF ABBREVIATIONS AND DEFINITION OF TERMS

AE	Adverse event
AUC _(controlled)	Area under the nicotine concentration-time curve calculated using linear trapezoidal summation from time zero (defined as the start of controlled use to 180 minutes, or the last quantifiable concentration during that interval).
AUC _(uncontrolled)	Area under the nicotine concentration-time curve calculated using linear trapezoidal summation from time 360 (defined as the start of uncontrolled use to 540 minutes, or the last quantifiable concentration during that interval).
BMI	Body mass index
CI	Confidence interval
C _{max} (controlled/uncontrolled)	Maximum measured plasma concentration during the controlled/uncontrolled use session
CRF	Case Report Form (may include electronic data capture systems or paper forms)
CSA	Clinical study agreement
DSM-IV-TR	Diagnostic and Statistical Manual of Mental Disorders, 4 th edition text revision
ECG	Electrocardiogram
EDC	Electronic data capture
E _{max_item}	Maximum reduction in VAS score for each item between pre-use and post-use (i.e., VAS _{pre-use} – VAS _{post-use})
E _{max_plst}	Maximum score for Pleasant VAS
E _{max_urge}	Maximum reduction “Urge to smoke” (Tobacco/Nicotine Withdrawal Questionnaire) between pre-use and post-use
ENDS	Electronic nicotine delivery system
FDA	Food and Drug Administration
FSH	Follicle Stimulating Hormone
GCP	Good Clinical Practice
HbsAg	Hepatitis B surface antigen
HCVA _b	Hepatitis C Antibody

HIV	Human Immunodeficiency Virus
ICF	Informed consent form
ICH	International Conference on Harmonisation
IRB	Institutional Review Board
Kel _(controlled/uncontrolled)	Apparent first-order terminal elimination rate constant calculated from a semi-log plot of the plasma concentration-time curve of the controlled/uncontrolled use session.
LSM	Least square mean
PK	Pharmacokinetic
QA	Quality assurance
SAE	Serious adverse event
SAP	Statistical analysis plan
SD	Standard deviation
T _{1/2(controlled)}	Apparent first-order terminal elimination half-life calculated as 0.693/Kel of the plasma concentration-time curve from time zero (defined as the start of controlled use) to 180 minutes.
T _{1/2(uncontrolled)}	Apparent first-order terminal elimination half-life calculated as 0.693/Kel of the plasma concentration-time curve from time zero (defined as the start of controlled use) to 540 minutes.
THC	tetrahydrocannabinol
T _{max(controlled/uncontrolled)}	Time of the maximum measured plasma concentration during the controlled /uncontrolled use session.
VAS	Visual analog scale
VLN	Very low nicotine
UDS	Urine drug screen

5. INTRODUCTION

5.1. Background

With the introduction of the 2009 Family Smoking Prevention and Tobacco Control Act, the Food and Drug Administration (FDA) was granted the authority to regulate tobacco products including the nicotine content of cigarettes. In July 2017, FDA Commissioner [name]., announced the FDA's intention to limit nicotine in cigarettes to minimally or non-addictive levels. During his announcement, [name] stated that it has long been known that nicotine is the primary addictive component of cigarettes and that if smokers lose their addiction to cigarettes, they will be free to choose when and how often to smoke. A key component in the FDA's announced plan is to provide current smokers who are unable or unwilling to quit using nicotine with other, less harmful, means to obtain it. In other words, to provide a migration route away from traditional cigarettes to other types of tobacco or nicotine products such as cigarettes based on heat not burn technology, traditional smokeless, Snus, or electronic nicotine delivery system (ENDS) products.

Historically, tobacco harm reduction initiatives have focused on efforts to prevent or reduce tobacco initiation rates, increase quit rates, and decrease recidivism. The proposed reduction of nicotine cigarettes is believed to represent a viable policy tool to impact cigarette initiation rates and cigarette quit rates. Studies conducted to date indicate that reducing the nicotine content of cigarettes to non-addictive levels would potentially limit the reinforcing effects of cigarettes. A number of recent studies suggests that cigarettes with very low nicotine (VLN) content are associated with a positive set of outcomes, including reductions in the number of cigarettes smoked, reductions in nicotine exposure and nicotine dependence, increased abstinence from smoking, reduced exposure to toxicants, and fewer adverse events (AEs) (Rupprecht et al., 2017; Donny et al., 2007; Donny et al., 2015; Benowitz et al., 2007; Benowitz et al., 2009; Benowitz et al., 2012; Hatsukami et al., 2013). These studies evaluated cigarettes with nicotine content ranging from 0.4 to 15.8 mg nicotine per gram of tobacco with the typical combustible cigarette tobacco content ranging from approximately 8 mg to 20 mg.

The cigarettes included in the reported studies were manufactured by 22nd Century Group, Inc. under contract to RTI/National Institute on drug Abuse (NIDA). 22nd Century Group, Inc. is currently evaluating the commercial potential of a menthol and non-menthol VLN cigarette (0.4 mg nicotine/gram of tobacco). It is anticipated that these cigarettes will provide similar benefits to a consumer that switches from their usual brand to the VLN cigarette as those reported in the literature (Rupprecht et al., 2017; Donny et al., 2007; Donny et al., 2015; Benowitz et al., 2007; 2009; 2012; Hatsukami et al., 2013).

5.2. Study Rationale

The purpose of the current study is to provide an abuse liability assessment of VLN cigarettes compared with own-brand cigarettes and nicotine polacrilex gum in current manufactured filtered king size cigarette smokers, as recommended in "FDA Draft Guidance for Industry

Modified Risk Tobacco Products ([March 2012](#))”. Results of this study may provide supporting evidence for lower abuse liability of VLN cigarettes relative to own-brand cigarettes.

6. STUDY OBJECTIVES

6.1. Primary Objective

The primary objective of the study is:

- To evaluate the abuse liability of VLN cigarettes (0.4 mg nicotine/gram of tobacco) relative to own-brand cigarettes and nicotine polacrilex gum under controlled use and uncontrolled use conditions.

6.2. Secondary Objectives

The secondary objectives of the study are:

- To compare the nicotine pharmacokinetic (PK) profiles of VLN cigarettes relative to own-brand cigarettes and nicotine polacrilex gum under controlled use and uncontrolled use conditions.
- To characterize product use behavior of VLN cigarettes, own-brand cigarettes, and nicotine polacrilex gum.

7. INVESTIGATIONAL PLAN

7.1. Overall Study Design and Plan

This study will be a randomized, two-part, 3-way crossover designed to evaluate the abuse liability, PK, and product use behavior associated with study products, including VLN cigarettes, subjects' own-brand cigarettes, and nicotine polacrilex gum in healthy adult male and female exclusive smokers. The study will consist of 3 phases: Screening, a Confined Assessment Phase consisting of product training session, Part A, and Part B, and an End of Study Phase.

7.1.1. Screening Phase (Visit 1)

The Screening Phase will be completed during a clinic visit within 28 days of the Confined Assessment Phase and will consist of a standard medical screen.

7.1.2. Confined Assessment Phase (Visit 2)

7.1.2.1. Check-in and Product Trial (Day -1)

Subjects who successfully complete the Screening Phase will return to the clinical unit on Day -1 for check-in and to complete a product trial session. Subjects will engage in a 10-minute product training session with the nicotine polacrilex gum in order to familiarize themselves with the "chew and park" method, which requires subjects to chew the gum until they experience a tingling sensation, park the gum between the cheek and gum until the tingling subsides, and then begin chewing again. On Day -1, subjects will also complete a training session on the pharmacodynamic questionnaires. Subjects will be required to abstain from using nicotine- and tobacco-containing products for approximately 20 hours prior to each product use session in Part A.

7.1.2.2. Part A (Day 1 to 3)

On Day 1, subjects will be randomized to one of three product sequence groups in Part A, which will consist of an ad libitum product use session of each of the following study products for 4 hours in a randomized crossover manner (one product per day):

- Product A: VLN cigarette
- Product B: Own-brand non-menthol cigarette
- Product C: Nicorette® Original Flavor™

A pharmacodynamic measure ("use product again" visual analog scale [VAS]) will be administered at the end of each ad libitum product use period and product use behaviors (i.e., number of units consumed, duration of gum in mouth) will be collected throughout each ad libitum product use period (See [Table 1](#)).

7.1.2.3. Part B (Day 4 to 6)

Upon completion of Part A, subjects will be randomized to one of three product sequence groups in Part B, which will consist of 3 study days (Days 4 to 6), with one product per day. Each study

day will consist of: 1) Controlled Product Use Session (10 puffs from their own-brand cigarette or VLN cigarette [maximum 3 ± 2 seconds per puff] at approximately 30 ± 5 -second interpuff intervals^a, or chew the nicotine polacrilex gum using the “chew and park” method for 10 minutes); and 2) Uncontrolled Product Use Session (use of one unit of a product ad libitum for 10 minutes). The Controlled Product Use Session and Uncontrolled Product Use Session will be separated by approximately 6 hours. During Part B, pharmacodynamic measures, PK samples, and product use behavior (Uncontrolled Product Use Session only) will be collected at various time points each day (See [Table 1](#)).

Safety assessments, including AEs, physical examinations, vital signs (respiratory rate, pulse rate, blood pressure, and oral temperature), electrocardiogram (ECG), clinical laboratory tests (clinical chemistry, hematology, urinalysis, and serology), urine drug screen (UDS), and alcohol test will be collected at designated time points throughout the study.

7.1.3. End of Study or Early Termination

Subjects will be discharged from the clinic on Day 6 once all procedures are completed (or at Early Termination).

The maximum duration of subject participation, including Screening will be approximately 5 weeks.

An overview of the study design is provided in [Figure 1](#).

Study assessments and procedures will be performed at the visits and time points outlined in the Schedule of Assessments ([Table 1](#)).

^a In the event that the subject completes the cigarette in less than 10 puffs, no additional cigarette will be provided.

Figure 1: Overview of Study Design

[figure not shown]

Table 1: Schedule of Assessments

	Screening	Check-in	Part A	Part B								End of Study/ET	
Assessment	Day:	-28 to -2	-1	1 to 3	4 to 6 (Daily controlled use and uncontrolled use sessions)								
Informed consent		X			Assessment timepoints (minutes ^a)								
Demographics		X											
Medical history		X											
Review of eligibility		X	X										
Physical examination		X	X ^b										X ^b
Height, weight, BMI		X											
HIV, Hepatitis B/C		X											
Pregnancy test		X ^c	X ^d										
FSH (post-menopausal women)		X											
Vital signs ^e		X	X										X
Oral temperature		X	X										X
12-lead ECG		X											X
Urine cotinine screen		X											
Urine drug and alcohol test		X	X										

^a All listed timepoints are minutes after the start of product use

^b Abbreviated (symptom-directed) physical examination performed at the investigator's discretion

^c Serum pregnancy test

^d Urine pregnancy test

^e Vital signs include respiratory rate, pulse rate and blood pressure

	Screening	Check-in	Part A	Part B														End of Study/ET
Day:	-28 to -2	-1	1 to 3	4 to 6 (Daily controlled use and uncontrolled use sessions)														6
Assessment				Assessment timepoints (minutes ^a)														
Clinical laboratory tests ^f	X																	X
Concomitant medications	X	X	X		<----- Recorded throughout ----->													X
AE Monitoring ^g	X	X	X		<----- Recorded throughout ----->													X
Randomization			pre ^h	pre ⁱ														
Product use		X ^j	X ^k		<0 ^l	-	-	-	>									
PK sampling ^m				pre	2	5	7	10	12	15	20	30	45	60	90	120	150	180
Pharmacodynamic Training/practice ⁿ		X																
Tobacco/Nicotine Withdrawal Questionnaire ^o				pre		5				15		30		60	90			

^f Clinical laboratory assessments include hematology, biochemistry, and urinalysis

^g Spontaneous AE reporting is continuous throughout the study, beginning with the time the subject gives informed consent; however, at regular intervals, AE checks will be performed using a non-leading question.

^h Day 1 only

ⁱ Day 4 only

^j Trial of 4 mg nicotine polacrilex gum for 10 minutes

^k Product use under ad libitum condition for 4 hours on each day

^l First product under controlled use condition manner (10 puffs [maximum 3 ± 2 seconds per puff] with approximately 30-second inter-puff-intervals for cigarettes and 10 minutes “chew and park” for nicotine polacrilex gum) and second product under uncontrolled use condition for approximately 10 minutes (ad libitum) with approximately 6 hours in between 1st and 2nd use sessions

^m Blood samples collected at same time points following the start of the 1st and 2nd product use sessions. Pre-product use samples should be collected within approximately 5 minutes prior to the start of product use, all other time points should be taken within ± 1 minute for the first 30 minutes and ± 5 minutes from the nominal time for all other time points (except when coinciding with PD testing). Actual time of blood draw will be recorded.

ⁿ Additional PD training sessions may be performed throughout the study, as necessary.

^o Administered at same time points following the start of the 1st and 2nd product use sessions

	Screening	Check-in	Part A	Part B										End of Study/ET	
Day:	-28 to -2	-1	1 to 3	4 to 6 (Daily controlled use and uncontrolled use sessions)										6	
Assessment				Assessment timepoints (minutes ^a)											
Direct Effects of Product Questionnaire ^b				pre		5			15		30		60	90	
Use the product again VAS			X ^b										90 ^b		
Amount of product used			X ^c	< ^d	-	-	-	>							
Tobacco cessation information														X	
Admission		X													
Discharge														X	

NOTE: Pre-use assessments (not including PK) may be conducted up to 60 minutes prior to product use. When assessments coincide at any given timepoint during a product use session, the order of assessments should be pharmacodynamics assessments followed by PK. The pharmacodynamic assessments should be conducted at the nominal timepoint (± 2 minutes up to 30 minutes postdose and ± 5 minutes postdose thereafter). AE=adverse event; BMI=body mass index; ECG=electrocardiogram; ET=early termination; FSH=follicle stimulating hormone; HIV=human immunodeficiency virus; pre=pre-use

^b Questionnaire administered at end of each product use session, within 10 minutes of completing the product use session (i.e., 4 hours \pm 10 minutes)

^c Number of units consumed and duration of gum in mouth

^d Uncontrolled Product Use Sessions only; number of inhalations per cigarette, duration of inhalations [per puff], duration of gum in mouth

7.2. Discussion of Study Design

The overall study design is consistent with similar publicly available clinical studies conducted with cigarettes, non-combustible nicotine products (i.e., e-cigarettes) or nicotine replacement therapy in that it will be conducted using a randomized, cross-over design. This approach controls for inter-individual variability with each subject acting as his/her own control ([Vansickel et al., 2010](#); [McPherson et al., 2016](#); [Stiles et al., 2017](#)). Randomization will be used to avoid bias in the assignment of subjects to order of product use, to increase the likelihood that known and unknown subject attributes (e.g., demographics and baseline characteristics) are evenly balanced across groups, and to enhance the validity of statistical comparisons across groups.

Subjects will be healthy current combustible manufactured filtered king size cigarette smokers, using their own-brand of cigarettes as the positive control. This should serve as the most highly reinforcing product for cigarette smokers and is more representative of a “real-world” scenario. Consistent with the “continuum of risk” of tobacco and nicotine products, which suggests that nicotine replacement therapies provide a lower risk of abuse ([Fagerstrom and Eissenberg, 2012](#)), addiction and harm relative to combustible cigarettes, this study will also include nicotine polacrilex gum as the negative control comparator. Nicotine polacrilex gum has been shown to have low to moderate reinforcing effects compared with combustible cigarettes ([Stiles et al., 2017](#)). Although traditional abuse liability studies of pharmaceutical products include a placebo comparator, the nature of the products in the current study will be apparent to the subjects, therefore, it is not possible to implement a true placebo control. Rather, the study includes both a positive and a negative control to test the sensitivity of the model, and to achieve a direct relative comparison of the abuse liability of VLN cigarettes to own-brand cigarettes and nicotine polacrilex gum.

The current study will include a pre-specified period of abstinence prior to each study product administration day (approximately 20 hours in Part A and prior to controlled-use session in Part B, and 6 hours between controlled and uncontrolled-use sessions in Part B) to minimize the impact that residual nicotine concentrations may have on baseline pharmacodynamic, PK and physiological measurements. Consistent with previously published studies, the current study will include an ad libitum product use session, which will allow the subject to use the product as they would in a “real-world” scenario with no limitation on amount of product used, for up to 4 hours. Controlled and uncontrolled product use sessions are also included in order to compare the pharmacodynamic effects and patterns of use under conditions where subjects are instructed on how to use the product (i.e., [maximum 3 ± 2 seconds per puff] at approximately 30 ± 5 -second interpuff intervals) versus how they would use the product in a typical situation.

The current study will use measures of urge to smoke, positive effects, intent to use the product again, and negative effects as proxy measures for the relative reinforcing efficacy of VLN cigarettes, own-brand cigarettes and 4 mg nicotine polacrilex gum. The ability of the VLN cigarettes to satisfy the urge to smoke over the short term will be assessed using the “Urge to Smoke” question in the Tobacco/Nicotine Withdrawal Questionnaire measure and positive effects will be assessed using the “Is the product ‘Pleasant’ right now?” question in the Direct Effects of Product Questionnaire; both will be administered as 100-point VAS. The “Use Product

Again” bipolar VAS has been included at the end of the ad libitum use session in Part A and 90 minutes after product use in Part B to evaluate overall reinforcement effects of the test products. Additional subjective effects will be assessed with “at-the-moment” VAS (Direct Effects of Product Questionnaire, Tobacco/Nicotine Withdrawal Questionnaire) during the Controlled and Uncontrolled Use Sessions to evaluate the magnitude, onset, and offset of product effects and withdrawal symptoms during and after controlled use of the study products.

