12.4.3.2. Part B

Responses to each Tobacco/Nicotine Withdrawal Questionnaire and Direct Effects of Product Questionnaire item will be summarized by time point for each study product, and product use condition. For Tobacco/Nicotine Withdrawal VAS scores, descriptive statistics (n, mean, SD, median, Q1, Q3, min, max) for the difference from pre-use at each time point will also be reported. Derived parameters (E_{max}) for each questionnaire item will be summarized using descriptive statistics.

A linear mixed effects model for analysis of variance/covariance (Proc Mixed) will be performed on $E_{max_urge(controlled)}$ and $E_{max_plst(controlled)}$. The model will include E_{max} as the response variable, sequence, study product, and period as fixed model effects, baseline score as a covariate (for E_{max_urge} only), and subject nested-within sequence as a random effect. Sequence will be tested using subject nested-within-sequence as the error term. Least square mean (LSM) and 95% confidence interval (CI) for each Study Product group will be provided. Comparisons will be made for Product A vs. B, A vs. C and B vs. C. The comparison between Product A and Product C will be used as a comparison for internal validity. The LSM difference, p-value and 95% CI of the difference will be provided.

The same model will be used for $E_{max_urge(uncontrolled)}$ and $E_{max_plst(uncontrolled)}$, and all E_{max} of other questions in the Tobacco/Nicotine Withdrawal Questionnaire and Direct Effects of Product Questionnaire for the controlled and uncontrolled product uses in Part B. Responses to Use the Product Again VAS will be summarized by study product using descriptive statistics (n, mean, SD, median, Q1, Q3, min, max). A summary table of frequencies may also be provided.

Descriptive statistics (n, mean, SD, median, Q1, Q3, min, max) will be provided on duration of time a product is used (time spent per cigarette and duration of gum in mouth), number of inhalations (puffs), and duration of inhalation (per puff) per cigarette for own-brand and VLN cigarettes.

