## 9. PHARMACOKINETIC AND PHARMACODYNAMIC ANALYSES

### Pharmacodynamic

#### VAS Scores

Responses to Tobacco/Nicotine Withdrawal and Direct Effects of the Product Questionnaires recorded as VAS scores will be treated as continuous variables. Data listings of VAS scores for each questionnaire item will be provided for each subject.

For the Tobacco/Nicotine Withdrawal questionnaire, the reduction in VAS score will be calculated using the difference between pre-use and post-use values at each time point for each treatment (i.e.  $VAS_{pre-use1} - VAS_{post-use1}$ ).

Responses to each Tobacco/Nicotine Withdrawal Questionnaire and Direct Effects of Product Questionnaire item, as well as the Tobacco/Nicotine Withdrawal reduction from pre-use, will be summarized by time point for each study product, and product use condition using the following descriptive statistics (n, mean, SD, median, Q1, Q3, minimum, maximum, CV%). Individual and mean figures for the responses to Tobacco/Nicotine Withdrawal Questionnaire (unadjusted and baseline adjusted) and Direct Effects of Product Questionnaire item will be presented using linear scale.

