#### PD Parameters

The following subjective effect parameters will be calculated for each subject and treatment:

Questionnaire	PD Parameter	Definition
Tobacco/Nicotine Withdrawal Questionnaire	$E_{max\_item(controlled)}$	The maximum reduction in VAS score for each item during the first product use in Part B
	$E_{max\_item(uncontrolled)}$	The maximum reduction in VAS score for each item during the second product use in Part B
Direct Effects of Product Questionnaire	$E_{max\_item(controlled)}$	The largest VAS score recorded for the response to each item during the first product use in Part B
	$E_{max\_item(uncontrolled)}$	The largest VAS score recorded for the response to each item during the second product use in Part B

The definition of the different item in each questionnaire is detailed in the table below.

Questionnaire	Item	Question
Tobacco/Nicotine Withdrawal Questionnaire	$E_{max\_urge(controlled)}$ $E_{max\_urge(uncontrolled)}$	Urge to smoke
	$E_{max\_anx(controlled)}$ $E_{max\_anx(uncontrolled)}$	Anxious
	$E_{max\_diffct(controlled)}$ $E_{max\_diffct(uncontrolled)}$	Difficulty Concentrating
	$E_{max\_impat(controlled)}$ $E_{max\_impat(uncontrolled)}$	Impatient
	$E_{max\_crav(controlled)}$ $E_{max\_crav(uncontrolled)}$	Craving a Cigarette

Direct Effect of Product	$E_{max\_plst}(\text{controlled})$	Is the product "Pleasant" right now?
	$E_{max\_plst}(\text{uncontrolled})$	
	$E_{max\_stf}(\text{controlled})$	Is the product "Satisfying" right now?
	$E_{max\_stf}(\text{uncontrolled})$	
	$E_{max\_calm}(\text{controlled})$	Is the product making you feel "Calm" right now?
	$E_{max\_calm}(\text{uncontrolled})$	
	$E_{max\_conc}(\text{controlled})$	Is the product helping you "Concentrate" right now?
	$E_{max\_conc}(\text{uncontrolled})$	
	$E_{max\_awake}(\text{controlled})$	Is the product making you feel more "Awake" right now?
	$E_{max\_awake}(\text{uncontrolled})$	
	$E_{max\_sick}(\text{controlled})$	Is the product making you feel "Sick" right now?
	$E_{max\_sick}(\text{uncontrolled})$	
	$E_{max\_hunger}(\text{controlled})$	Is the product reducing your "Hunger" for food right now?
	$E_{max\_hunger}(\text{uncontrolled})$	
	$E_{max\_more}(\text{controlled})$	Would you like "More" of the product right now?
	$E_{max\_more}(\text{uncontrolled})$	

The items  $E_{max\_urge}(\text{controlled})$  and  $E_{max\_plst}(\text{controlled})$  will be the primary endpoints of the study while the remaining items will be secondary endpoints.

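### Part B ratings are collected partly to evaluate onset and offset, but Emax is the only rating parameter compared between products, so how long an effect lasts gets no between-product estimate

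*Protocol*

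**What the plan says.** Protocol section 7.2 gives the purpose of the at-the-moment scales, which are used in both Part B sessions, as follows: "evaluate the magnitude, onset, and offset of product effects and withdrawal symptoms during and after controlled use of the study products". Table 1 (Protocol 7.1.3, SAP Appendix A) schedules both questionnaires before use and at 5, 15, 30, 60 and 90 minutes, with the footnote "Administered at same time points following the start of the 1st and 2nd product use sessions".

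The SAP (section 9, PD Parameters) derives one value per item and session. For withdrawal items it is "The maximum reduction in VAS score for each item during the first product use in Part B". For direct-effect items it is "The largest VAS score recorded for the response to each item during the first product use in Part B". Matching definitions cover the second product use.

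The inferential analysis in Protocol 12.4.3.2 uses that value alone: "The model will include E_{max} as the response variable, sequence, study product, and period as fixed model effects". It is then extended to "all E_{max} of other questions in the Tobacco/Nicotine Withdrawal Questionnaire and Direct Effects of Product Questionnaire for the controlled and uncontrolled product uses". The individual readings "will be summarized by time point for each study product, and product use condition using the following descriptive statistics" (SAP section 9, VAS Scores), and mean and individual curves are planned. SAP section 12 declares no change to the protocol analyses.

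**The concern.** Of the three purposes named in section 7.2, only magnitude has a derived parameter and a between-product difference with an interval. Emax is the best of five post-use readings. A product whose relief has faded by 30 minutes can score the same as one whose relief holds to 90.

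This matters most for VLN against own-brand. Both are smoked by the same 10-puff procedure in the controlled session, so similar early relief with different persistence is plausible. The plan also treats nicotine more fully than the ratings: plasma AUC is compared by mixed model, and Tmax and T1/2 by Hodges-Lehmann (Protocol 12.4.4, SAP section 9). If the rating curves separated after the peak, there would be no planned estimate of the gap, and SAP section 6 would label one produced after lock post hoc and exploratory.

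**Working it through.** **1. The plan's own figure.** Protocol 12.2 gives a difference of 15.85, SD 28.44 and 54 completers for Emax_urge, with two-sided alpha 0.05. Read 28.44 as a per-product SD with no within-subject correlation:
- SD of the difference = √2 × 28.44 = 40.22.
- Noncentrality = 15.85 × √54 / 40.22 = 2.90, which gives power 81.1%. The smallest n for 80% is 53, so 54 is reproduced closely.
- Read instead as the SD of the paired difference, n would be 28 and power at 54 about 98%.

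The Pleasant calculation also rests on Emax. The documents give no mean or SD for any duration measure, so the rest is illustration.

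**2. Assumed curves.** Both products relieve 40 points at 5 minutes. Relief at time t = 40 × 2^(−(t−5)/h), where h is the half-life.

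| h (min) | 5 | 15 | 30 | 60 | 90 |
|---|---|---|---|---|---|
| 60 | 40.0 | 35.64 | 29.97 | 21.19 | 14.98 |
| 30 | 40.0 | 31.75 | 22.45 | 11.22 | 5.61 |
| 20 | 40.0 | 28.28 | 16.82 | 5.95 | 2.10 |

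Also assumed: independent reading noise SD 12, an additive session SD of 25, and 54 paired subjects.

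**3. Emax.** P(max ≤ x) = ∏ Φ((x − m_j)/12) over the five readings, before the session shift. Numerical integration gives expected Emax of 46.6, 44.2 and 42.9 for h = 60, 30 and 20. Adding the session variance 25² gives per-product SDs of 26.6, 26.8 and 26.9, near the plan's 28.44.
- 60 vs 20: difference 3.7 (a simulation of 200,000 pairs gave 3.6), SD √(26.6² + 26.9²) = 37.8, noncentrality 3.7 × √54 / 37.8 = 0.72, power 11%.
- 60 vs 30: difference 2.4, SD 37.7, noncentrality 0.47, power 7%.

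**4. Time-averaged relief, 0 to 90 minutes.** Relief is zero at time 0. The trapezoid weights are 7.5, 12.5, 22.5, 30 and 15 minutes, divided by 90.
- 60 vs 20: (12.5 × 7.35 + 22.5 × 13.15 + 30 × 15.24 + 15 × 12.88) / 90 = 11.5 (simulation 11.4).
- 60 vs 30: (12.5 × 3.89 + 22.5 × 7.52 + 30 × 9.96 + 15 × 9.37) / 90 = 7.3.
- The weights sum to 0.972 and their squares to 0.228. The per-product variance is 25² × 0.972² + 12² × 0.228 = 623.5, so the SD of the difference is √(2 × 623.5) = 35.3.
- Noncentralities are 2.40 and 1.52, which give powers of 65% and 32%.

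**5. Sensitivity.** If session variation scales the curve (assumed CV 25/40) instead of shifting it, the time-averaged powers rise to about 99% and 71%, against 10% and 7% for Emax. With different assumed mean curves (0/30/40/38/32/26 against 0/30/40/28/12/4 at 0, 5, 15, 30, 60 and 90 minutes), both peaks are 40 and the areas are 2930 and 1775 point-minutes. With session and reading SDs of 14 to 20 each, Emax rejects in about 25% to 30% of simulations and the area in about 86% to 99%.

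**The case against.** The strongest reply is that section 7.2 says evaluate, not test. It is a design rationale. The objectives mention neither onset nor offset, and the endpoint lists define the Part B rating endpoints as Emax throughout. Nothing promised has been dropped. The time course is also reported: statistics at every time point by product and session, six mean-curve figures and individual profiles. Relief that ended by 30 minutes would show there. All of this stands. What is missing is an estimate with an interval, not the information.

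The sentence in section 7.2 is also introduced as covering additional subjective effects, after a separate sentence that gives the urge and Pleasant items their own purpose, and its aim mentions controlled use only. One can therefore argue that the onset and offset aim was not meant for the two primary items or for the uncontrolled session. The point is open, because the questionnaires and sessions it names include them.

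Two wider readings are tempting. A reader might infer that the whole plan compares peaks only. It does not, because nicotine AUC, Tmax and T1/2 are compared. A reader might also take the power figures as a forecast. They are not, because the curves, noise and session SDs are all assumed. Under the less favourable additive case the time-averaged measure would itself miss the difference about two times in three.

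**Conclusion.** The gap is real but modest. For the Part B ratings, Emax is the only parameter with a between-product estimate, and it cannot separate brief from sustained relief. Onset and offset are described only.

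The documents do not support the inference that the primary analysis is faulty, or that a duration difference would be hidden. Emax is a coherent primary endpoint and the planned curves would display such a difference. The consequence is narrower: no planned estimate of its size, and a post hoc label on any comparison devised after lock.

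In the additive illustration with 54 subjects, power is about 11% for Emax and 65% for the time average (half-lives 60 and 20 minutes), or 7% and 32% (60 and 30). These figures rest on equal 5-minute peaks, exponential decay and the assumed SDs. They show that Emax can be insensitive to duration, not that it will be here. The change is worth considering; it is not essential.

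**What to change.** Keep Emax primary. In SAP section 9, PD Parameters, add for the urge and Pleasant items, in each Part B session, a time-averaged effect to 90 minutes by linear trapezoid on actual times. Use the reduction from that session's pre-use score for urge and the post-use score for Pleasant. State where the Pleasant integration starts and what happens when the last reading is missing, since nothing is imputed. Analyse it with the existing mixed model, with the same covariate rule as Emax for that item. Report A−B, A−C and B−C differences with 95% intervals, labelled supportive. If the printed PD code is reused, its A-versus-B line needs correcting: it repeats the A-versus-C coefficients.

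I would not add time of Emax. On a five-point grid about 40% of pairs tie under the assumed additive model, and it marks the peak, not the offset.

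The cost is SAP wording, four model fits and their output, with no new data. It adds 2 items × 2 sessions × 3 contrasts = 12 unadjusted intervals to the 13 × 2 × 3 = 78 Emax contrasts already planned, and duration is cut off at 90 minutes. If the sponsor prefers no new parameter, one sentence in section 7.2 saying that onset and offset are described only would align the text with the analysis.
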